8.1.3. Temporary Discontinuation

Temporary discontinuation of study treatment is not allowed. Participants who discontinue study treatment will not be considered withdrawn from the study and should attend the TOC and Follow-up Visits.

8.1.4. Rechallenge

8.1.4.1. Study Treatment Restart or Rechallenge

Study treatment restart or rechallenge after liver chemistry stopping criteria are met by any participant in this study is not allowed.

8.2. Withdrawal from the Study

- A participant may withdraw from the study at any time at his/her own request, or may be withdrawn at any time at the discretion of the investigator for safety, behavioral, compliance, or administrative reasons.
- Reasons for study withdrawal include:
 - Participant lost to follow-up
 - Participant withdrew consent
 - Termination of the study by GSK
 - Investigator discretion
- If the participant withdraws consent for disclosure of future information, the sponsor may retain and continue to use any data collected before such a withdrawal of consent.
- If a participant withdraws from the study, he/she may request destruction of any samples taken and not tested, and the investigator must document this in the site study records.
- Refer to [Table 1](#) for data to be collected at the time of study discontinuation and follow-up and for any further evaluations that need to be completed.

8.3. Lost to Follow-Up

A participant will be considered lost to follow-up if he or she repeatedly fails to return for scheduled visits and is unable to be contacted by the study site.

The following actions must be taken if a participant fails to return to the clinic for a required study visit:

- The site must attempt to contact the participant and reschedule the missed visit as soon as possible and counsel the participant on the importance of maintaining the assigned visit schedule and ascertain whether or not the participant wishes to and/or should continue in the study.
- Before a participant is deemed lost to follow-up, the investigator or designee must make every effort to regain contact with the participant (where possible, 3 telephone calls and, if necessary, a certified letter to the participant's last known mailing address or local equivalent methods). These contact attempts should be documented in the participant's medical record.
- Should the participant continue to be unreachable, he/she will be considered to have withdrawn from the study with a primary reason of lost to follow-up.

9. STUDY ASSESSMENTS AND PROCEDURES

- Study procedures and their timing are summarized in [Table 1](#) and [Table 2](#).
- Protocol waivers or exemptions are not allowed.
- Immediate safety concerns should be discussed with the sponsor immediately upon occurrence or awareness to determine if the participant should continue or discontinue study treatment.
- Adherence to the study design requirements, including those specified in [Table 1](#) and [Table 2](#), is essential and required for study conduct.
- All screening evaluations must be completed and reviewed to confirm that potential participants meet all eligibility criteria. The investigator will maintain a screening log to record details of all participants screened and to confirm eligibility or record reasons for screening failure, as applicable.
- Procedures conducted as part of the participant's routine clinical management (e.g., blood count) and obtained before signing of ICF may be utilized for screening or baseline purposes provided the procedure met the protocol-specified criteria and was performed within the time frame defined in [Table 1](#).
- If assessments are scheduled for the same nominal time, THEN the assessments should occur in the following order:

1. 12-lead ECG
2. Vital signs
3. Pharmacokinetic and bacteriology urine specimen collection
4. Pharmacokinetic and safety blood draws

Note: The timing of the assessments should allow the blood draw to occur at the exact nominal time.

- The maximum amount of blood collected from each participant over the duration of the study, including any extra assessments that may be required, will not exceed 500 mL.
- Repeat or unscheduled samples may be taken for safety reasons or for technical issues with the samples.
- Participants will be confined to the clinic from Baseline through the On-Therapy Visit. Participants will return to the clinic for the TOC and Follow-up Visits.

Note: At the discretion of the investigator, for emergency purposes only, participants may temporarily leave the clinic on study days without serial PK collections and only at times that do not interfere with required study assessments. Participants will be instructed to follow the protocol restrictions. The investigator will ensure the participant is eligible to continue in the study upon return to the clinic. All doses of study treatment will be administered under site staff supervision in the clinic.

The study will comprise the following visits and clinical procedures:

Clinic Confinement Visits

- **Baseline (Day -1 to Day 1 predose) Visit:** The Baseline Visit includes a screening window of up to 24 hours from the time of informed consent to the first dose of study treatment. Baseline assessments performed during the screening window do not need to be repeated before study treatment is started unless indicated as a Day 1 predose assessment in [Table 1](#).

Baseline assessments will be performed, including the following (see [Table 1](#)):

- Participants will provide a pretreatment clean-catch midstream urine sample for confirmation of pyuria (≥ 10 WBC/mm³ or the presence of leukocyte esterase) and/or nitrite per local laboratory procedures.

Note: Repeat baseline urine samples are allowed if contamination, defined as ≥ 10 squamous epithelial cells, is observed under microscopic evaluation.

- Site staff will record clinical signs and symptoms of acute cystitis ([Appendix 10](#)), clinical laboratory samples will be collected, vital signs will be measured, and a triplicate 12-lead ECG and complete physical examination will be performed.
- Participants who meet the eligibility criteria in time to support the first dose of study treatment by 2 PM will be admitted to the clinic on Day 1 and On-Therapy procedures will begin. Participants who meet the eligibility criteria past the first dose time limit of 2 PM may be admitted that same day (Day -1) or the next morning (Day 1); dosing will start on the morning of Day 1.

Day 1 predose assessments will be performed (see [Table 1](#) and [Table 2](#)), including the following:

- An ECG will be performed and vital signs will be measured if the baseline assessment was not within 4 hours of the first dose of study treatment.
 - Participants will provide a pretreatment clean-catch midstream urine sample for Gram stain, quantitative bacteriology culture, and antimicrobial susceptibility testing.
 - Predose blood and urine PK samples will be collected.
 - A stool microbiome specimen will be obtained from participants who consent to provide such specimens.
 - Vaginal and pharyngeal swab microbiome specimens will be obtained from participants who consent to provide such specimens.
- **On-Therapy (Day 1 to Day 5) Visit:** Participants will be confined to the clinic during the 5-day On-Therapy Visit period, and will receive oral gepotidacin 1500 mg BID for 5 days (total of 10 doses) starting with the first dose on Day 1. All doses of study treatment will be administered under site staff supervision and

all doses will be administered with food (i.e., standardized meals or snacks as applicable).

- The first dose of gepotidacin must be administered by 2 PM on Day 1 and subsequent doses will be administered approximately every 12 hours.
- Only if medically appropriate per the investigator's judgement, for participants who are enrolled after 2 PM, the first dose of study treatment will be postponed until the next morning; nonexclusionary pain medication will be allowed for these participants before study treatment is started.
- Study assessments and PK collections on Days 1 through 5 will be performed relative to the time-matched dose as determined by the first dose of study treatment (e.g., if the first dose is at 11 AM on Day 1 for a participant, then their time-matched dose on subsequent days will be at 11 AM; or, if the first dose is at 1 PM on Day 1 for a participant, then their time-matched dose on subsequent days will be at 1 PM).
- On Day 1, a single 12-lead ECG will be performed at 2 hours after the first dose of study treatment. On Day 4, a single 12-lead ECG will be performed at predose and 2 hours postdose (at the same ECG time points as on Day 1) (see [Table 2](#)).
- Vital sign measurements will be taken daily from Days 2 through 5.
- On Days 2 through 5, before the time-matched dose, clinical signs and symptoms of acute cystitis will be recorded ([Appendix 10](#)) and participants will provide a clean-catch midstream urine sample for Gram stain, quantitative bacteriology culture, and antimicrobial susceptibility testing.
- Blood and urine PK collection (see [Table 1](#), [Table 2](#), and [Section 9.5.1](#)).
- On Day 3, clinical laboratory samples will be collected for hematology, chemistry, and urinalysis.
- On Day 4, at predose and at approximately 2 hours postdose, cervical, rectal, and pharyngeal swab PK specimens will be obtained from participants who consent to provide such specimens.
- On Day 5, a stool microbiome specimen will be obtained from participants who consent to provide such specimens.
- On Day 5, vaginal and pharyngeal swab microbiome specimens will be obtained from participants who consent to provide such specimens.
- On Day 5, after all study procedures have been performed, including a predose clean-catch midstream urine sample for Gram stain, quantitative bacteriology culture, and antimicrobial susceptibility testing, predose PK sample collections, and safety assessments, participants will be discharged from the clinic. Participants should remain in the clinic to complete a total of 10 doses. Participants will be instructed to return for the TOC (Day 10 to 13) and Follow-up (Day 28±3) Visits.

- At any time during the study, participants experiencing new or continuing signs and symptoms of acute cystitis will be assessed and treated per the investigator's judgement. If a participant is switched to a different antibiotic before or during the TOC Visit, all TOC procedures should be completed before the other antibiotic is started. Any participant who discontinues from the PK portion of the study should return for the TOC and Follow-up Visits.

Outpatient Visits

- **TOC (Day 10 to 13) Visit:** Participants will return for the TOC Visit 5 to 8 days after completion of study treatment. Clinical signs and symptoms of acute cystitis will be recorded ([Appendix 10](#)) and samples for Gram stain, quantitative bacteriology culture, and antimicrobial susceptibility testing will be collected. Safety assessments will be performed and AEs and concomitant medication use will be recorded.
- **Follow-up (Day 28) Visit:** Participants will return for the Follow-up Visit 28 (± 3) days after the start of study treatment. Clinical signs and symptoms of acute cystitis will be recorded ([Appendix 10](#)) and samples for Gram stain, quantitative bacteriology culture, and antimicrobial susceptibility testing will be collected. Adverse events and concomitant medication use will be recorded. A stool microbiome specimen will be obtained from participants who consent to provide such specimens. Vaginal and pharyngeal swab microbiome specimens will be obtained from participants who consent to provide such specimens.

9.1. Efficacy Assessments

Efficacy is an exploratory assessment in this study. Please refer to Section [9.5](#) for the primary PK assessments.

9.1.1. Therapeutic Response Evaluation

Therapeutic response (success/failure) is a measure of the overall efficacy response. A therapeutic success refers to participants who have been deemed both a “microbiological success” (see Section [9.1.2.1](#)) and a “clinical success” (i.e., “responders”) (see Section [9.1.3](#)). All other combinations (other than clinical success + microbiological success) will be deemed failures for therapeutic response.

Therapeutic response will be determined by statistical programming for TOC and Follow-up Visits.

9.1.2. Bacteriology Samples

At the Baseline Visit (predose on Day 1), a pretreatment, clean-catch midstream urine sample must be obtained from all participants for Gram stain, quantitative bacteriological culture, and in vitro antimicrobial susceptibility testing. For inclusion in the micro-ITT Population (Section [10.2](#)), a baseline qualifying bacterial uropathogen (defined in [Appendix 9](#)) is required. At the On-Therapy (Days 2 through 5 only), TOC, and Follow-up Visits, a clean-catch midstream urine sample will be obtained and sent to a

central laboratory for Gram stain, quantitative bacteriological culture, and in vitro antimicrobial susceptibility testing. Identification and susceptibility testing of isolates recovered from urine specimens at all visits will also be conducted at a designated laboratory. Additional tests, as needed, to further characterize recovered isolates will also be performed by a designated laboratory. Instructions for sample collection, processing, and shipment are provided in the SRM and the laboratory manual. The study site should follow the Microbiology Procedures section of the laboratory manual to minimize potential contamination of the specimens.

9.1.2.1. Microbiological Outcome and Response

Only those participants who have a qualifying bacterial uropathogen (defined in [Appendix 9](#)) identified at Baseline will be evaluated for microbiological outcome and response. The microbiological outcome and response to study treatment will be determined by prespecified programmed algorithm for each participant/pathogen.

The microbiological outcome is determined by comparing the baseline culture results to the culture results at each subsequent visit (see [Table 3](#), [Table 4](#), and [Table 5](#)). The corresponding microbiological response (success or failure) “by pathogen” is then assigned, as shown in [Table 4](#) and [Table 5](#). Participant level microbiological response is a measure of the combined “by pathogen” response(s). Participant level microbiological success refers to participants who have been deemed a “microbiological success” for all of their “by pathogen” microbiological responses. All other combinations (other than all “microbiological successes”) are deemed failures for participant level microbiological response. Participant level microbiological response will be determined by statistical programming.

Table 3 Microbiological Outcome by Pathogen at the On-Therapy Visit

Defining Criteria	Outcome

 Any participant that receives administration of an alternative or additional antibacterial therapy during the On-Therapy Visit will be assigned a microbiological outcome of "unable to determine" from that day onward. 	

A quantitative urine culture taken during the On-Therapy Visit (Days 2 through 5 only) shows that the qualifying bacterial uropathogen recovered at Baseline is reduced to $<10^3$ CFU/mL
	Microbiological eradication

A quantitative urine culture taken during the On-Therapy Visit (Days 2 through 5 only) shows that the qualifying bacterial uropathogen recovered at Baseline grows $\geq 10^3$ CFU/mL
	Microbiological persistence

A determination of the baseline qualifying bacterial uropathogen microbiological outcome cannot be made (e.g., no urine culture taken, sample lost, etc.)
	Unable to determine

A new qualifying bacterial uropathogen, not identified at Baseline, is documented by quantitative urine culture during the On-Therapy Visit (Days 2 through 5 only) in a participant who is a clinical failure or unable to determine
	Superinfection

A new qualifying bacterial uropathogen, not identified at Baseline, is documented by quantitative urine culture at the On-Therapy Visit (Days 2 through 5 only) in a participant who is a clinical success
	Colonization

CFU=colony-forming units.

Table 4 Microbiological Outcome and Response by Pathogen at the Test-of-Cure Visit

Defining Criteria	Outcome	Response

 Any participant that receives administration of an alternative or additional antibacterial therapy before the TOC Visit will be assigned a microbiological outcome of "unable to determine" and a response of "microbiological failure." Participants considered microbiological failures at the TOC Visit will also be considered microbiological failures at the Follow-up Visit. 		
A quantitative urine culture taken at the TOC Visit shows reduction of the qualifying bacterial uropathogen recovered at Baseline to $<10^3$ CFU/mL	Microbiological eradication	Microbiological success
A quantitative urine culture taken at the TOC Visit shows that the qualifying bacterial uropathogen recovered at Baseline, and which was also shown to persist at the On-Therapy Visit, grows $\geq 10^3$ CFU/mL	Microbiological persistence	Microbiological failure
A quantitative urine culture taken at the TOC Visit shows that the qualifying bacterial uropathogen recovered at Baseline, and which was also shown to be eradicated at the On-Therapy Visit, grows $\geq 10^3$ CFU/mL	Microbiological recurrence	Microbiological failure
A determination of the baseline qualifying bacterial uropathogen microbiological response cannot be made (e.g., no urine culture taken, sample lost, etc.)	Unable to determine	Microbiological failure
A new qualifying bacterial uropathogen, not identified at Baseline, is documented by quantitative urine culture at the TOC Visit in a participant who is a clinical failure	New infection	Microbiological failure
A new qualifying bacterial uropathogen, not identified at Baseline, is documented by quantitative urine culture at the TOC Visit in a participant who is a clinical success	Colonization	Microbiological success

CFU=colony-forming units; TOC=Test-of-Cure.

Table 5 Microbiological Outcome and Response by Pathogen at the Follow-Up Visit

Defining Criteria	Outcome	Response

 Any participant that receives administration of an alternative or additional antibacterial therapy before the Follow-up Visit will be assigned a microbiological outcome of “unable to determine” and a response of “microbiological failure.” Participants considered microbiological failures at the TOC Visit will also be considered microbiological failures at the Follow-up Visit. 		
A quantitative urine culture taken at the Follow-up Visit shows reduction of the qualifying bacterial uropathogen recovered at Baseline to $<10^3$ CFU/mL	Sustained microbiological eradication	Microbiological success
A quantitative urine culture taken at the Follow-up Visit shows that the qualifying bacterial uropathogen recovered at Baseline grows $\geq 10^3$ CFU/mL	Microbiological recurrence	Microbiological failure
A determination of the baseline qualifying bacterial uropathogen microbiological response cannot be made (e.g., no urine culture taken, sample lost, etc.)	Unable to determine	Microbiological failure
A new qualifying bacterial uropathogen, not identified at Baseline, is documented by quantitative urine culture at the Follow-up Visit in a participant who is a clinical failure	New infection	Microbiological failure
A new qualifying bacterial uropathogen, not identified at Baseline, is documented by quantitative urine culture at the Follow-up Visit in a participant who is a clinical success	Colonization	Microbiological success

CFU=colony-forming units; TOC=Test-of-Cure.

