2. SCHEDULE OF ACTIVITIES

Table 1 Schedule of Activities

Visit Study Day	Baseline (includes a screening window of up to 24 hours before the first dose of study treatment)		On-Therapy					Test-of-Cure	Follow-up
	-1	1	2	3	4	5 ^a	10 to 13	28±3	
Procedure	Predose	Postdose							
Written informed consent	X								
Inclusion and exclusion criteria	X								
Admission to clinic	X								
Participant demography	X								
Physical examination (including height and weight at Baseline only)	X					X	X		
Medical/surgical history	X								
Diagnosis of presumptive acute cystitis ^b	X								
Bacteriology samples ^c		X		X	X	X	X	X	
Record acute cystitis signs and symptoms ^d	X			X	X	X	X	X	
12-lead ECG ^e	X	X ^f	X		X				
Vital sign measurements ^g	X	X ^f		X	X	X	X	X	
Hematology, chemistry, and urinalysis	X				X		X	X	
Serology (hepatitis B and C and HIV) ^h	X								
Pregnancy test ⁱ	X						X	X	
Administer study treatment ^j			X ^j	X	X	X	X ^j		
Blood and urine PK sampling ^k		X	X	X	X	X	X		
Cervical, rectal, and pharyngeal PK sampling (optional) ^l						X			
Genetic sample (optional)		X ^m							
Stool microbiome collection (optional) ⁿ		X					X	X	
Vaginal and pharyngeal microbiome collection (optional) ⁿ		X					X	X	
Serious adverse events ^{o,p}	X	X	X	X	X	X	X	X	
Adverse events ^o			X	X	X	X	X	X	
Concomitant medications	X	X	X	X	X	X	X	X	
Discharge from clinic							X ^{a,j}		
Schedule/Reminder for next outpatient visit							X ^q	X ^r	

ECG=electrocardiogram; HIV=human immunodeficiency virus; PK=pharmacokinetic; TOC=Test-of-Cure; WBC=white blood cell.

- a. If a participant discontinues during the on-treatment confinement period, Day 5 assessments will be completed before the participant is discharged, with the exception of study treatment administration.
- b. Based on confirmation of pyuria (≥ 10 WBC/mm³ or the presence of leukocyte esterase) and/or nitrite from a pretreatment clean-catch midstream urine sample per local laboratory procedures. Note: Repeat baseline urine samples are allowed if contamination, defined as ≥ 10 squamous epithelial cells, is observed under microscopic evaluation.
- c. Participants will provide a clean-catch midstream urine sample pretreatment at Baseline (predose on Day 1), predose on Days 2 through 5 (i.e., before the time-matched dose); and at the TOC and Follow-up Visits for Gram stain, quantitative bacteriology culture, and in vitro antimicrobial susceptibility testing.

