- d. Site staff will record clinical signs and symptoms of acute cystitis based on participant interview (see [Appendix 10](#)).
- e. Obtain a triplicate 12-lead ECG in semi-supine position at Baseline only. See [Table 2](#) for single 12-lead ECG predose and postdose assessment time points on Days 1 and 4.
- f. Only repeat the ECG and vital sign assessments at predose on Day 1 if the baseline assessment was not within 4 hours of the first dose of study treatment.
- g. Take measurement of temperature, blood pressure, and pulse rate in semi-supine position.
- h. If serology testing was performed within 3 months prior to the first dose of study treatment and results were positive, testing at Baseline is not required. If testing was performed within 3 months and any result was negative, testing at Baseline is required.
- i. For women of childbearing potential, a negative serum pregnancy test is needed for eligibility at Baseline. A urine pregnancy test may be performed on Day 5 and at the TOC Visit.
- j. The first dose on Day 1 will only be administered after all baseline procedures have been completed. All doses of study treatment will be administered under site staff supervision and all doses will be administered with food (i.e., standardized meals or snacks as applicable). Participants should remain in the clinic to complete a total of 10 doses.
- k. See [Table 2](#) for serial collection time points. Predose PK blood samples will be collected before each time-matched dose on Days 1 through 5. Predose PK urine samples will be collected 0 to 2 hours before each time-matched dose on Days 1 through 5. Only 1 sample is needed when serial and predose samples overlap. If a participant is switched to a different antibiotic before the end of study treatment, a final blood and urine PK sample should be collected prior to administration of the different antibiotic.
- l. Collection of cervical, rectal, and pharyngeal swab PK specimens is optional. Specimens will be collected on Day 4 at predose and at approximately 2 hours postdose. The 2-hour postdose collection should be as close as possible to the 2-hour postdose blood PK draw time on Day 4.
- m. Collect sample only if the participant has a signed consent specific for this purpose. Baseline (predose on Day 1) is the recommended time to collect the sample, but it can be collected at any time during the study.

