- Urine quantitative bacteriology culture results will be summarized and plotted by visit and qualifying uropathogens isolated at baseline

Table 4 Microbiological Outcome by Qualifying Uropathogen at the On-Therapy Visit

Defining Criteria	Outcome

 ● Any participant that receives administration of an alternative or additional antibacterial therapy during the On-Therapy visit will be assigned a microbiological outcome of “unable to determine” from that day onward. 	

 ● A quantitative urine culture taken during the On-Therapy Visit (Days 2 through 5 only) shows that the qualifying bacterial uropathogen recovered at Baseline is reduced to <10³ CFU/mL 	
 ● Microbiological eradication

 ● A quantitative urine culture taken during the On-Therapy Visit (Days 2 through 5 only) shows that the qualifying bacterial uropathogen recovered at Baseline grows ≥10³ CFU/mL 	
 ● Microbiological persistence

 ● A determination of the baseline qualifying bacterial uropathogen microbiological outcome cannot be made (e.g., no urine culture taken, sample lost, etc.) 	
 ● Unable to determine

 ● A new qualifying bacterial uropathogen, not identified at Baseline, is documented by quantitative urine culture during the On-Therapy Visit (Days 2 through 5 only) in a participant who is a sponsor-determined clinical failure or unable to determine 	
 ● Superinfection

Defining Criteria	Outcome

 A new qualifying bacterial uropathogen, not identified at Baseline, is documented by quantitative urine culture at the On-Therapy Visit (Days 2 through 5 only) in a participant who is a sponsor-determined clinical success 	
 Colonization

CFU=colony-forming units

Table 5 Microbiological Outcome and Response by Qualifying Uropathogen at the Test-of-Cure Visit

Defining Criteria	Outcome	Response

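### The on-therapy antibacterial override works by calendar day, so a culture taken earlier that day, before the other drug, loses its derived Day 2–5 microbiological outcome

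*Protocol*

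**What the plan says.** **The rule.** Protocol section 9.1.2.1, Table 3, opens with an override: a participant given alternative or additional antibacterial therapy on therapy "will be assigned a microbiological outcome of 'unable to determine' from that day onward". SAP section 9.1.1.1, Table 4, carries it over: a participant who "receives administration of an alternative or additional antibacterial therapy during the On-Therapy visit will be assigned a microbiological outcome of" *unable to determine*, again from that day. Neither table exempts a culture collected earlier on the same day.

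**What the culture would otherwise show.** A Day 2–5 culture that "shows that the qualifying bacterial uropathogen recovered at Baseline grows" at 10³ CFU/mL or more is persistence, and below that it is eradication. A new qualifying uropathogen is superinfection or colonization, depending on the clinical outcome. The same table also uses *unable to determine* where no determination is possible ("e.g., no urine culture taken, sample lost, etc").

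**When samples are taken.** Footnote c of the Schedule of Activities sets the on-therapy bacteriology sample at "predose on Days 2 through 5 (i.e., before the time-matched dose". For a switch before or during the Test-of-Cure (TOC) Visit, Protocol section 9 says that "all TOC procedures should be completed before the other antibiotic is started"; those procedures include a quantitative culture. Footnote k adds that "a final blood and urine PK sample should be collected prior to administration of the different antibiotic".

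**Later visits.** Protocol Tables 4 and 5 apply their override by sequence: therapy given before the visit. The response is then microbiological failure, and failure at TOC carries to Follow-up.

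**The concern.** The override exists because another antibacterial makes a later culture unreadable as evidence on gepotidacin. A culture collected before that drug does not have this problem, even on the same date. The day-level wording sweeps it in, although the protocol asks for samples before a switch and although Tables 4 and 5 work by sequence.

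The Day 2–5 microbiological outcome is a named exploratory endpoint, under the objective on time to eradication (Protocol section 4; SAP section 2.2). On the switch day, the derived table cannot tell a woman with persistent growth from one whose culture was already negative, and puts both with women whose sample was lost. Superinfection shows this clearly. Table 3 requires a new uropathogen in a clinical failure (or in a woman whose clinical outcome is undetermined), and use of another antimicrobial for the current infection makes her a clinical failure (Table 6). Yet the override prevents superinfection from being assigned that day.

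**Working it through.** The plan gives no figure to reproduce here, so the check is a reading of the text followed by simple proportions.

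**Step 1: can a pre-switch culture exist on the switch day?** Yes, but this is not guaranteed. The daily culture is tied to the gepotidacin dose, which in the protocol's own example may be at 1 PM. A switch that morning would come before it. No passage orders the daily culture ahead of a switch; only the instruction on TOC procedures places a culture before the other antibiotic.

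**Step 2: which displays change?** The Day 2–5 part of SAP Table 2.1 (microbiological outcome) and the eradication curve in SAP Figure 2.1. These do not change:
- bacterial counts by visit (SAP Table 2.2, Figure 2.2 and Listing 14);
- TOC and Follow-up microbiological response, which is failure under either coding;
- therapeutic response, which is therefore also failure.

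**Step 3: size for one switched woman.** Assume one qualifying uropathogen per woman and *unable to determine* kept in a denominator of N. Keeping her pre-switch culture moves one day's share by 1/N. Later days stay *unable to determine* under both rules.

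| Assumed N | 1/N, percentage points |
|---|---|
| 10 | 10.0 |
| 15 | 6.7 |
| 20 | 5.0 |
| 30 | 3.3 |

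**Step 4: direction, with N = 20.**

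*Her culture is at or above 10³ CFU/mL; 18 others eradicated, 1 other persistent.*
- Current rule: eradication 18/20 = 90.0%, persistence 1/20 = 5.0%, undetermined 1/20 = 5.0%.
- Amended rule: eradication 18/20 = 90.0%, persistence 2/20 = 10.0%, undetermined 0.

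*Her culture is below 10³ CFU/mL; 19 others eradicated.*
- Current rule: eradication 19/20 = 95.0%.
- Amended rule: eradication 20/20 = 100.0%.

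The current rule therefore understates persistence in the first case and eradication in the second.

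**Step 5: dependence on the denominator.** The documents do not say whether *unable to determine* stays in the on-therapy denominator. If it were dropped, the first case would give 18/19 = 94.7% eradication against 90.0%. Only then does the current rule raise the eradication percentage.

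**The case against.** The strongest defence is that a day-level rule is the one the collected data can support. Protocol section 7.7 asks for start and end dates of other medication, not times. Without a time, a culture taken after the other drug could be scored as gepotidacin eradication, and the rule prevents that. Nor is the label misused: the tables define *unable to determine* explicitly for other antibacterial therapy as well as for absent cultures. This stands as a reason to keep the day rule as a fallback. It does not justify overriding a culture known to have come first.

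A reader might infer more than the documents support:
- *That the result is recorded as missing, or cannot be recovered.* The counts are still summarized, plotted and listed, so growth or no growth on the switch day can be seen. Only the derived category is lost.
- *That gepotidacin failure is hidden.* On-therapy days carry an outcome and no success or failure response. She is a failure at TOC, at Follow-up and for therapeutic response.
- *That the rule favours gepotidacin.* It overrides eradication as readily as persistence. The documents do not say that switched women mostly have persistent growth. Protocol section 8.1 also allows treatment to stop, and alternative therapy to start, for adverse events or at the investigator's discretion.

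**Conclusion.** The point holds in a narrow form. Protocol Table 3 and SAP Table 4 misclassify a valid culture collected on the switch day before the other antibacterial, because they test the date and not the order of events. The consequence is confined to exploratory, descriptive Day 2–5 displays, in a study that tests no hypothesis. Each such woman moves one day's outcome share by 1/N, either way.

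The figure of 5 points assumes N = 20 and one qualifying uropathogen per woman. The documents state neither the micro-ITT size nor how many women will be switched, and if nobody is switched nothing changes. That the TOC result is unaffected rests on treating a switch during Days 2–5 as therapy before the TOC Visit, even when TOC procedures are brought forward to the switch day. This is a worthwhile clarification, not a threat to the trial's conclusions.

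**What to change.** - **Both tables.** In Protocol Table 3 and SAP Table 4, apply the override only to cultures collected after the first dose of the other antibacterial. A culture collected before that dose keeps its observed outcome, including on the same day.
- **Data.** Record the start time of any antibacterial given during confinement. Where it is missing, keep the day-level rule.
- **Denominator.** State that *unable to determine* stays in the micro-ITT denominator for the on-therapy percentages.
- **No other change.** Leave the TOC and Follow-up failure rules as they are, and say that they apply even when TOC procedures are done early on the switch day. If a daily culture and an early TOC culture both precede the switch, state which one supplies that day's on-therapy outcome.

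The cost is one data field and a short edit to each document. No extra samples are needed, and the choice and timing of any other antibiotic are untouched.
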